### **4.3. Withdrawal Criteria and Procedures**

A subject may withdraw from study treatment at any time at his/her own request, or may be withdrawn at any time at the discretion of the investigator for safety, behavioral or administrative reasons.

Should a subject fail to attend the clinic for a required study visit, the site should attempt to contact the subject and re-schedule the missed visit as soon as possible. The site should also counsel the subject on the importance of maintaining the assigned visit schedule and ascertain whether or not the subject wishes to and/or should continue in the study based on previous non-compliance. In cases where the subject does not return for the rescheduled visit or cannot be reached to reschedule the missed visit, the site should make every effort to regain contact with the subject (3 telephone calls and if necessary a certified letter to the subject's last known mailing address) so that they can appropriately be withdrawn from the study.

These contact attempts should be documented in the subject's medical record. Should the subject continue to be unreachable, then and only then will he/she be considered to have withdrawn from the study with a primary reason of "Lost to Follow-up". For all other subjects withdrawing from the study, an alternative reason for discontinuation should be recorded in the Case Report Form (CRF). If a subject prematurely withdraws from participation in the study for any reason, the investigator/sub-investigator must make every effort to assess the items specified on discontinuation test.

Refer to Section 5.2.1 for Liver Chemistry stopping criteria, Section 5.2.2 for QTc withdrawal and Section 7.2 for Pregnancy.

Liver chemistry threshold stopping criteria have been designed to assure subject safety and to evaluate liver event etiology (in alignment with the Food and Drug Administration [FDA] premarketing clinical liver safety guidance). See Section 5.2.1 for details.

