**Table 3 Time assessment window of the each PK sample collection**

Study Day	Hrs relative to dose	Blood sampling for PK
Day 0: pre-dose	Day 0 pre-dose	-60 minutes
Day 0: 5min	5min after dose completion	± 1 minutes
Day 0: 1hour	1 hour after dose completion	± 10 minutes
Day 0: 6 hour	6 hour after dose completion	± 15 minutes
Day 0: 24 hour	24 hour after dose completion	± 1 Hrs
Day 1	48 hour after dose completion	± 2 Hrs
Day 7	192 hour after dose completion	-48Hrs to +2 Hrs
Day 14	360 Hrs after dose completion	-48Hrs to +2 Hrs
Day 21	528 Hrs after dose completion	-48Hrs to +2 Hrs
Day 28	696 Hrs after dose completion	-48Hrs to +2 Hrs
Day 42	1032 Hrs after dose completion	-48Hrs to +2 Hrs
Day 56	1368 Hrs after dose completion	-48Hrs to +2 Hrs
Day 84	2040 Hrs after dose completion	-48Hrs to +2 Hrs

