## **9. DATA ANALYSIS AND STATISTICAL CONSIDERATIONS**

Full details of tabulation/analyses will be described in the "Reporting Analysis Plan" (RAP).

Any changes from analyses described within this protocol will be stated in "RAP" and "Final Clinical Study Report"

If the study is prematurely discontinued, all available data will be listed and a review will be carried out to assess which statistical analyses are still considered appropriate.

Data obtained for this study and used for statistical analysis will be examined for outliers, and their accuracy will be verified or queried. Values verified as accurate will be included in the analysis.

All categorical data will be summarized by reporting the frequency and percentage of subjects in each cohort.

All continuous data will be summarized using mean, standard deviation, median, ranges, and 95% confidence interval (CI) where applicable.

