**9.3.4.2.2. Pharmacokinetic Parameters**

Serum concentration-time data for GSK1550188 will be analyzed by non-compartmental methods using WinNonlin 5.2 or above. Calculations will be based on the actual dose and sampling dates and times recorded during the study. From the concentration-time data for GSK1550188, the following pharmacokinetic parameters will be determined: maximum concentration (Cmax), area under the plasma concentration-time curve [AUC(0-t) and AUC(0-∞)], and apparent terminal phase half-life (t1/2), terminal phase elimination rate (λz), systemic clearance (CL), and volume of distribution (Vz). Summary statistics for the above parameters will be calculated.

For each of the derived serum GSK1550188 pharmacokinetic parameters, the following summary statistics will be calculated: median, minimum, maximum, arithmetic mean, standard deviation, coefficient of variation, geometric mean, 95% confidence interval for the geometric mean and standard deviation of logarithmically transformed data.

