5.7.1. Permitted Medications	For subjects with a history of allergies, allergic responses to food, drugs or insects, or a history of urticaria, antihistamine and acetaminophen should be administered prophylactically.	For subjects with a history of allergies, allergic responses to food, drugs or insects, or a history of urticaria, antihistamine and acetaminophen may be <del>should be</del> administered prophylactically.	Clarify “should be” is a recommendation; it helps reduce the risk of a reaction for those patients who have a history of allergies.
Section 5.7.2 Prohibited Medications and Non-drug Therapies		Add: From 30 days prior to Day 0 
 
• Live vaccine
 
	To keep consistency with the new addition of exclusion criteria 21.

Section	Previous Text	Revised Text	Rationale
Section 6 STUDY ASSESSMENTS AND PROCEDURES	
Paragraph2:
 
The end time of the infusion will be designated Time 0, and subsequent PK sampling and safety assessments will be performed relative to this time. When several procedures are scheduled at the same nominal time point, PK blood sampling should be given priority.
	
Add:
 
The time assessment window of the each PK blood sample collection is shown in Table 3. The end time of the infusion will be designated Time 0, and subsequent PK sampling and safety assessments will be performed relative to this time. It is essential that the exact time of blood sampling, however, should still be accurately recorded. The safety assessments are recommended to be conducted close to PK sample collection; however, when several procedures are scheduled at the same nominal time point, PK blood sampling should be given priority.
 
Add:
 
Table 3 Time assessment window of the each PK sample collection
	
Add Table 3 to clarify the allowed time-window for PK sample collection.

Section 6 Study assessments and Procedures		
In Table 2, Add:
 
Inclusion/Exclusion criteria check at pre-dose on Day 0
	
To allow using pulse rate monitoring to replace heart rate monitoring if subject has sinus rhythm which is

Section	Previous Text	Revised Text	Rationale

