2. REPORTING & ANALYSIS PLAN SYNOPSIS

Overview	Key Elements of the Reporting and Analysis Plan
Purpose	
The purpose of this Reporting and Analysis Plan (RAP) is to describe:
 
 All planned analyses and outputs required for the final Clinical Pharmacology Study Report (CPSR) of study 200909
Protocol	
 This RAP is based on the protocol (Dated: 26/JAN/2016) of study 200909 (GSK Document Number 2013N175219_00).
Primary Objective	
 To investigate the pharmacokinetics (PK) of intravenously (IV) administered GSK1550188 10 mg/kg in Chinese subjects with SLE.
Secondary Objective	
 To evaluate the safety and tolerability of GSK1550188 in Chinese subjects with SLE. To investigate the effect of GSK1550188 on pharmacodynamics (PD) of B cell subsets.
Primary Endpoint	
 Serum concentrations and the derived pharmacokinetic parameters of GSK1550188: C_{max}, t_{1/2}, AUC(0-t), AUC(0-∞), λ_z, CL and V_z.
Secondary Endpoint	
 Safety and tolerability endpoints: adverse events, vital sign, 12-lead ECG, and clinical laboratory safety tests B cell subsets (CD20+, CD20+/27+ memory, CD20+/27-naïve, CD20+/69+ activated, CD20+/138+ plasmacytoid, CD19+/27BRIGHT/38BRIGHT SLE subset and CD20-/138+ plasma cells)
Study Design	
 Multicenter, single dose study of intravenous GSK1550188 at a dose of 10 mg/kg Chinese subjects with SLE. A medical screen within 30 days prior to the first dose. Subjects will receive the dose on Day 0 and be kept in the study center up to 24 hours post dosing with subsequent outpatient visits occurring on Days 1, 7, 14, 21, 28, 42, 56, and 84.
Planned Analyses	
 No interim analyses are planned. The final planned analyses will be performed after all subjects have completed the study and after database freeze (both the CRF data and PK data).
Analysis	
 The 'Safety' Population (Comprised of subjects who receive at least

Overview	Key Elements of the Reporting and Analysis Plan

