8.1.3. Pharmacokinetic Parameters

- Refer to [Appendix 3: Data Display Standards & Handling Conventions \(Section 11.3.3 Reporting Process & Standards\)](#).

- The pharmacokinetic parameters will be calculated by standard non-compartmental analysis according to current working practices and using WinNonlin 6.3 or above.
- All calculations of non-compartmental parameters will be based on actual sampling times.
- If data permits, population PK modelling will be conducted and independent PK modelling plan document may be provided.
- Pharmacokinetic parameters described as following and in [Table 4](#) will be determined from intravenously (IV) administered GSK1550188, as data permits.

Table 4 Derived Pharmacokinetic Parameters

Parameter	Parameter Description
AUC(0-∞)	Area under the concentration-time curve from time zero (pre-dose) extrapolated to infinite time
AUC(0-t)	Area under the concentration-time curve from time zero (pre-dose) to last time of quantifiable concentration
CL	Clearance
C _{max}	Maximum observed concentration
λ _z	Terminal phase rate constant
t _{1/2}	Terminal phase half-life
V _z	Volume of distribution after intravenous administration

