
 • Reporting for Data Listings: 
 ○ Planned and actual time relative to study drug dosing will be shown in listings (Refer to IDSL Statistical Principle 5.05.1). ○ Unscheduled or unplanned readings will be presented within the subject's listings. ○ Visits outside the protocol defined time-windows (i.e. recorded as protocol deviations) will be included in listings but omitted from figures, summaries and statistical analyses. 	
Unscheduled Visits	

 • Unscheduled visits will not be included in summary tables. • Unscheduled visits will not be included in figures. • All unscheduled visits will be included in listings. 	
Descriptive Summary Statistics	
Continuous Data	Refer to IDSL Statistical Principle 6.06.1
Categorical Data	N, n, frequency, %
Reporting of Pharmacokinetic Concentration Data	
Descriptive Summary Statistics	Refer to IDSL Statistical Principle 6.06.1 Refer to GUI_51487 Any plasma concentrations below the assay lower limit of quantification (NQ) will be imputed using the following rules: 
 • NQs at the beginning of a subject profile (i.e. before the first incidence of a measurable concentration) are deemed to be zero as it is assumed that in this circumstance no drug is yet measurable in the plasma. • For NQs at the end of the subject profile (i.e. after the last incidence of a measurable concentration): 
 (1) for individual plots and pharmacokinetic analyses these are dropped (set to missing) as they do not provide any useful information (and can erroneously indicate that absolutely no drug is present) (2) for summary statistics these are set to 0 (to avoid skewing of the summary statistics) • Individual NQs which fall between two measurable concentrations are set to missing (individual values of this nature are assumed to be an anomaly) • More than one consecutive NQ between measurable concentrations are set to 0. • Measurable concentrations after more than one consecutive mid-profile NQ (a mid-profile NQ is defined as any NQ where measurable concentrations exist both before and after that NQ in the profile): For summary, these will be set to missing. For individual plot, no action will be done. • All NQs will remain as "NQ" in listings.

Reporting Standards	
Reporting of Pharmacokinetic Parameters	

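### The SAP's out-of-window omission rule predates the PK sampling windows and, as written, removes validly timed late concentrations from plots and summaries, and arguably from the NCA

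*SAP*

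**What the plan says.** - **Omission rule.** SAP 11.3.3, planned and actual time: "Visits outside the protocol defined time-windows (i.e. recorded as protocol deviations) will be included in listings but omitted from figures, summaries and statistical analyses".
- **Time basis of the NCA.** SAP 8.1.3: "All calculations of non-compartmental parameters will be based on actual sampling times"; SAP 11.4.4 repeats this. Protocol 9.3.4.2.2: "Calculations will be based on the actual dose and sampling dates and times recorded during the study".
- **Data to be analysed.** Protocol 9.3.2 puts all available data into the data sets.
- **Windows.** Protocol Table 3 allows PK samples on Days 7 to 84 from 48 h before to 2 h after a nominal hour, which for Day 84 is "2040 Hrs after dose completion". The amendment log gives the reason: "Add Table 3 to clarify the allowed time-window for PK sample collection".
- **Version.** SAP Section 2: "This RAP is based on the protocol (Dated: 26/JAN/2016) of study 200909 (GSK Document Number 2013N175219_00". Amendment 01 is dated 15 March 2017.
- **Missed visits.** Protocol 4.3: "the site should attempt to contact the subject and re-schedule the missed visit as soon as possible". No limit on the delay is given.

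**The concern.** The usual reason for dropping an off-schedule concentration is that it would be averaged under the wrong nominal time. NCA does not have that problem when each sample enters at its recorded time. The omission rule nevertheless carries no exception for it. It was also drafted before any tabulated PK window existed, and it now acts on an asymmetric window that Amendment 01 supplied later. Meanwhile the protocol asks sites to make up missed visits, which produces late samples.

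Two things are at stake. The first is plain on the text: late but correctly timed concentrations disappear from the individual profiles and from the concentration summary. The second depends on interpretation. SAP Section 8 is headed as the primary statistical analyses and contains the PK parameters, so a programmer could apply the rule to the NCA input as well. Another programmer could rely on SAP 8.1.3 and keep the samples. The same data would then give two sets of primary parameters, and the terminal-phase samples would matter most.

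**Working it through.** **1. The plan's own precision figure, for scale.** Inputs from protocol 9.2.1: n = 12, CV 20.0% (Cmax) and 32.1% (AUC(0-inf)). Upper bound on the log scale: exp(t(0.975, n−1) × √ln(1+CV²) / √n) − 1.
- Cmax: exp(2.201 × 0.1980 / 3.464) − 1 = 13.4%.
- AUC(0-inf): exp(2.201 × 0.3132 / 3.464) − 1 = 22.0%.

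Both match the protocol.

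**2. Where the windows close.** From Day 7 on, the nominal hours in protocol Table 3 equal (day + 1) × 24.

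| Visit | 24 × day (h) | Nominal (h) | Window (h) | Relative to 24 × day |
|---|---|---|---|---|
| Day 7 | 168 | 192 | 144 to 194 | −24 to +26 h |
| Day 56 | 1344 | 1368 | 1320 to 1370 | −24 to +26 h |
| Day 84 | 2016 | 2040 | 1992 to 2042 | −24 to +26 h |

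A visit 24 h late is in window and a visit 48 h late is out. The Day 84 window closes at 2042 / 24 = 85.1 days.

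**3. Effect on one subject if the rule reaches the NCA.** Protocol 1.1.2 gives a terminal half-life of 19.4 days at 10 mg/kg and a distribution half-life of 1.1-1.8 days. The assumed inputs are a bi-exponential curve c(t) = A·exp(−αt) + (1−A)·exp(−βt) with A from 0.3 to 0.6.

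Worked case, A = 0.3 and distribution half-life 1.1 days:
- β = ln 2 / 19.4 = 0.0357 per day.
- Total AUC = A/α + (1−A)/β = 0.476 + 19.592 = 20.068.
- Share beyond day 85: 19.592 × exp(−85β) / 20.068 = 19.592 × 0.0480 / 20.068 = 4.7%.
- Share beyond day 57: 19.592 × 0.1305 / 20.068 = 12.7%.
- Change in AUC(0-t): (1 − 0.127) / (1 − 0.047) − 1 = −8.4%.

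NCA with the log trapezoid and λz from the last three points, over the four corner cases:

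| Distribution half-life (d) | A | Extrapolated share, all samples | Extrapolated share, no Day 84 | Change in AUC(0-t) |
|---|---|---|---|---|
| 1.1 | 0.3 | 4.7% | 12.7% | −8.4% |
| 1.1 | 0.6 | 4.3% | 11.8% | −7.8% |
| 1.8 | 0.3 | 4.6% | 12.5% | −8.3% |
| 1.8 | 0.6 | 4.1% | 11.3% | −7.4% |

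Noise-free AUC(0-inf) does not move when Day 84 is dropped. It also changes by 0.0% if the Day 84 sample is taken 3 days late and kept at its actual time.

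**4. Precision of half-life.** With an assumed residual error of 10%, the SD of log half-life rises from 0.095 to 0.147 without Day 84. With 20% it rises from 0.196 to 0.325.

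**5. Group level.** One affected subject among 12 moves the geometric mean AUC(0-t) by ln(1 − 0.074)/12 to ln(1 − 0.084)/12, that is by −0.6% to −0.7%.

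**The case against.** **The rule does not name parameter derivation.** This is the strongest point. In the same block of SAP 11.3.3, the planned-time rule lists derived parameters separately from figures, summaries and statistical analyses, and the omission rule leaves them out. SAP 8.1.3 (derivation) is also kept apart from 8.1.4 (statistical analyses), and the specific text bases NCA on actual times. This stands: a reader might infer that the SAP discards late samples from the primary derivation, but it does not say so. It is one possible reading beside the Section 8 heading. The objection does not reach the individual plots and summaries, which the rule names by type.

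**The 2 h limit looks harsher than it is.** A reader might conclude that almost every make-up visit is lost. Step 2 shows otherwise, since a next-day visit can still be in window.

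**Non-PK data.** A reader might infer that a late Day 84 visit also loses its B-cell, laboratory, ECG and vital-sign results. Protocol Table 3 covers PK samples only, and the protocol gives no comparable post-dose window table for the rest. The loss is conditional on someone applying a PK window to the whole visit. The trigger is also a recorded deviation, under a deviation management plan that is not among the documents.

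**The verified-values sentence.** Protocol 9 says "Values verified as accurate will be included in the analysis", but as the end of an outlier check. It is not a rule on timing and carries little weight here. Protocol 9.3.2 is the better reference.

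**Timing deviations are to be assessed.** SAP 11.3.3 says their impact will be assessed as appropriate. That softens the rule but does not say which samples are used.

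**The effect is small for the group.** This is true for the mean (step 5) in a descriptive study without hypothesis tests.

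**Conclusion.** The point holds as a gap between the SAP and the amended protocol, with one definite and one conditional consequence. Definite: on the text, concentrations from visits roughly two or more days late leave the individual plots and the concentration summaries, although they stay in the listings. Conditional: the rule can be read to remove them from the NCA, against the actual-time basis in both documents and against protocol 9.3.2.

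Under that reading, a lost Day 84 sample costs the affected subject about 7-8% of AUC(0-t), raises the extrapolated share from about 4-5% to 11-13%, and makes half-life less precise. AUC(0-inf) stays unbiased without noise. No Cmax effect is shown, and samples from Day 7 on would not normally set Cmax after an infusion. The size rests on the assumed curve, its intercept split and the residual error. The documents do not give a rate of late visits, so no expected number of lost samples can be stated. The correction is cheap and removes an unplanned choice over how primary PK parameters are derived.

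**What to change.** Update SAP 11.3.3 to protocol Amendment 01 and state that:

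1. Omission of out-of-window samples applies only to nominal-time concentration displays (SAP Table 3.1 and Figures 3.2-3.3).
2. NCA and individual plots use every valid concentration at its recorded actual time, in window or not.
3. B-cell, laboratory, ECG and vital-sign results are not omitted because a PK sampling window was missed.

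The cost is a few sentences of SAP text and no new data. The nominal-time summaries and the parameter derivation will then use slightly different sample sets, which needs a footnote. Repeating SAP Table 3.2 without the out-of-window samples is optional.

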6. Pregnancy should be assessed with a blood test at Screening and with a urine test during the treatment period. Pregnancy beyond Day 84 and within 16 weeks after last dose of IP will be assessed with a homekit and subjects can report the results via phone to site.
7. Biomarkers include immunoglobulins, B cell subsets (CD20+, CD20+/27+ memory, CD20+/27-naïve, CD20+/69+ activated, CD20+/138+ plasmacytoid, CD19+/27BRIGHT/38BRIGHT SLE subset and CD20-/138+ plasma cells).
8. Only immunoglobulins (IgG, IgM and IgA) and auto antibodies (anti-dsDNA, ANA).
9. Includes subject history to be reported on CRF regarding any general signs or symptoms of infection.
10. The recommended date of "Admission to the Unit" and "Discharge" is only a suggestion. The subject can be admitted to unit from Day -2 to Day 0 and/or discharged on Day 1 based on site flexibility and resource allocation.
11. If a subject prematurely withdraws for any reason, the investigator must make every effort to assess the items specified on discontinuation test.

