#### **6.2.2. Clinical Laboratory**

Blood and urine will be taken for clinical laboratory test at screening and at pre-dose, and Days 0, 1, 14, 28, 56 and 84 post-dose.

- Hematology: WBC, RBC, Hb, Ht, PT, PTT, platelet count and WBC-differential (including ESR on screening)
- Chemistry: AST, ALT, ALP, GGT, LDH, creatinine, BUN, total bilirubin, total protein, albumin, uric acid, glucose, sodium, potassium, magnesium, chloride, carbon dioxide, calcium, phosphate (including CRP on screening)
- Urinalysis: protein, glucose, ketones, occult blood, microscopic examination
- Spot urine for proteinuria assessment

Note: ALT and/or AST elevations of greater than 2.5 x ULN will require Hepatitis B assessment, see Section [6.2.1.1](#)

All clinical laboratory blood samples will be sent to a central laboratory for analysis (details provided in the SPM). The central laboratory will fax laboratory results to the Investigator and will transmit the results electronically to GlaxoSmithKline.

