## 12. APPENDICES

### 12.1. Appendix 1: Liver Safety Process

The procedures listed below are to be followed if a subject meets the liver chemistry stopping criteria defined in Section 5.2.1:

- Notify the GSK medical monitor within 24 hours of learning of the abnormality to confirm the subject's study treatment cessation and follow-up.
- Complete the "Safety Follow-Up Procedures" listed below.
- Complete the liver event case report forms. If the event also meets the criteria of an SAE (see Section 7.1.3), the SAE data collection tool will be completed separately with the relevant details.
- Upon completion of the safety follow-up withdraw the subject from the study unless further safety follow up is required
- Do not restart study treatment
- Refer to the Flow chart for a visual presentation of the procedures listed below.

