11.5. Appendix 5: Premature Withdrawals & Handling of Missing Data

11.5.1. Premature Withdrawals

Element	Reporting Detail
General	
 • Subject study completion (i.e. as specified in the protocol) was defined as completion of all the phases of the study including the follow up visit. • Withdrawn subjects were not replaced in the study. • All subjects who withdraw prematurely from the study will be documented and the reason for their withdrawal recorded in the final Clinical Pharmacology Study Report (CPSR). • All available data from subjects who were withdrawn from the study will be listed and all available planned data will be included in summary, tables and figures, unless otherwise specified. • In the event that the study is prematurely discontinued, all available data will be listed and a review carried out by the study team to assess which statistical analyses are still considered appropriate and population approach may be used to deal with such situations as appropriate.

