11.8.5. Safety Tables

Safety Tables					
No.	Population	IDSL / TST ID / Example Shell	Title	Programming Notes	Deliverable [Priority]
Adverse Events					
2.01	Safety	CP_AE1p	Summary of All Adverse Events		SAC [1]
2.02	Safety	CP_AE1p	Summary of all adverse events by maximum intensity		SAC [1]
2.03	Safety	CP_AE1p	Summary of Drug-Related Adverse Events		SAC [1]
2.04	Safety	CP_AE1p	Summary of all drug-related adverse events by maximum intensity		SAC [1]
2.05	Safety	CP_AE1p	Summary of Serious Adverse Events		SAC [1]
2.06	Safety	CP_AE1p	Summary of Adverse Events Leading to Withdrawals from Study		SAC [1]
Labs					
2.07	Safety	LB1	Summary of Chemistry Laboratory Values		SAC [1]
2.08	Safety	LB1	Summary of Hematology Laboratory Values		SAC [1]
2.09	Safety	UR3	Summary of Urinalysis Dipstick Results		SAC [1]
2.10	Safety	LB1	Summary of Immonoglobulin		SAC [1]
2.11	Safety	LB1	Summary of Change from Baseline in Chemistry Laboratory Values		SAC [1]

Safety Tables					
No.	Population	IDSL / TST ID / Example Shell	Title	Programming Notes	Deliverable [Priority]
2.12	Safety	LB1	Summary of Change from Baseline in Hematology Laboratory Values		SAC [1]
2.13	Safety	LB1	Summary of Percent Change from Baseline in Immonoglobulin	Including the mean of baseline value	SAC [1]
2.14	Safety	SAFE_T1	Worst Laboratory Toxicity Grade: Chemistry		SAC [1]
2.15	Safety	SAFE_T1	Worst Laboratory Toxicity Grade: Hematology		SAC [1]
2.16	Safety	SAFE_T1	Worst Laboratory Toxicity Grade: Urinalysis		SAC [1]
2.17	Safety	SAFE_T1	Worst Laboratory Toxicity Grade: Immonoglobulin		SAC [1]
2.18	Safety	SAFE_T2	Laboratory Toxicity Grade Worsening of at Least 2 Grades from Baseline: Chemistry		SAC [1]
2.19	Safety	SAFE_T2	Laboratory Toxicity Grade Worsening of at Least 2 Grades from Baseline: Hematology		SAC [1]
2.20	Safety	SAFE_T2	Laboratory Toxicity Grade Worsening of at Least 2 Grades from Baseline: Urinalysis		SAC [1]
2.21	Safety	SAFE_T2	Laboratory Toxicity Grade Worsening of at Least 2 Grades from Baseline: Immunoglobulin		SAC [1]

Safety Tables					
No.	Population	IDSL / TST ID / Example Shell	Title	Programming Notes	Deliverable [Priority]
ECG					
2.22	Safety	EG2	Summary of ECG Parameter	Use latest assessment in case of multiple assessments at any given time point	SAC [1]
2.23	Safety	EG2	Summary of Mean Change from Baseline in ECG Values		SAC [1]

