11.9. Appendix 9: Example Mock Shells for Data Displays

Data Display Specification will be made available on Request.

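### As written, the SAP's visit and averaging rules let the worst-grade and 2-grade-worsening laboratory tables show a lower grade than was observed, most clearly for chemistry (Tables 2.14 and 2.18)

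*SAP*

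**What the plan says.** Four rules decide which records reach a laboratory summary table.

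- SAP 11.3.3, on unscheduled visits: "Unscheduled visits will not be included in summary tables". They appear in listings only, and no exception is attached.
- SAP 11.3.3, on timing: visits outside the protocol's windows are listed but left out of summaries.
- SAP 11.4.1: several measurements at one time point are averaged. If more were taken than specified, those closest to the planned time are used.
- SAP 11.5.1, for withdrawn subjects: everything is listed, but "all available planned data will be included in summary, tables and figures, unless otherwise specified".

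SAP 11.8.5 then lists Tables 2.14 to 2.17, for example "Worst Laboratory Toxicity Grade: Chemistry", and Tables 2.18 to 2.21, for example "Laboratory Toxicity Grade Worsening of at Least 2 Grades from Baseline: Chemistry". Each set covers chemistry, hematology, urinalysis and immunoglobulin.

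Protocol 6.2.2 fixes the laboratory schedule: "Blood and urine will be taken for clinical laboratory test at screening and at pre-dose, and Days 0, 1, 14, 28, 56 and 84". Table 2 of the protocol agrees on Days 14, 28, 56 and 84 and adds a discontinuation visit. Immunoglobulins follow the biomarker row ("Biomarkers include immunoglobulins, B cell subsets"), on Days 14, 28, 42, 56 and 84.

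Protocol 6.2.1 and Appendix 1 order further liver chemistries once ALT reaches 3 x ULN. These are weekly in general, and twice weekly when bilirubin or INR is also raised. Appendix 1 adds: "Upon completion of the safety follow-up withdraw the subject from the study unless further safety follow up is required".

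**The concern.** A table titled as the worst grade should show the worst grade seen. Off-schedule laboratory values tend to arise because a scheduled value was abnormal, so they are a likely place for a peak. A rule that drops or averages them works against the purpose of the table.

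The restriction is sensible for by-visit summaries, where an extra draw has no column. It does not suit a maximum taken over follow-up. Clinical laboratory safety is a secondary endpoint, so these tables are part of what the study reports on it.

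**Working it through.** The plan gives no figure on this point, so there is none to reproduce. The check covers the rules, then the calendar, then the grades.

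**1. Do the rules reach these tables?** SAP Table 5 marks the toxicity-grade rows of all four panels as summary tables. The programming notes for Tables 2.14 to 2.21 are blank. Table 2.22 in the same list does carry a record-selection note, so that column is where an exception would be expected. SAP Appendix 6 gives the grading source and the high/low split, but not which records feed the worst grade. No exemption appears in the text supplied.

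**2. Direction.** The worst grade is max g(x) over post-dose records. A maximum over a subset cannot exceed the maximum over the full set. A mean lies between its smallest and largest value, and grades rise away from normal in each direction, so the grade of a mean cannot exceed the worst single grade. With assumed ALT values of 3.2 and 6.0 x ULN at one time point, the mean is (3.2 + 6.0)/2 = 4.6. That is Grade 2, while the larger value is Grade 3. For the worsening tables, baseline is held fixed.

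**3. Calendar.** Repeats start 7 days after the trigger and run to Day 84. Scheduled chemistry days after Day 14 are 28, 56 and 84.

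| Trigger | Weekly repeats | On a scheduled chemistry day | Off schedule |
|---|---|---|---|
| Day 14 | (84 − 14)/7 = 10 | 3 (Days 28, 56, 84) | 7 of 10 |
| Day 28 | (84 − 28)/7 = 8 | 2 (Days 56, 84) | 6 of 8 |
| Day 56 | (84 − 56)/7 = 4 | 1 (Day 84) | 3 of 4 |

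This is an upper case. Monitoring ends once values settle, and protocol 6.2.1 steps down to twice monthly after four weeks if they have fallen. Days 21 and 42 are visits without planned chemistry. If a repeat drawn then were filed under that visit, the shares would be 5 of 10, 5 of 8 and 3 of 4.

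**4. When does a grade change?** Protocol Appendix 3 grades transferases as 1 (1.25 to 2.5 x ULN), 2 (above 2.5 to 5), 3 (above 5 to 10) and 4 (above 10). Table 2.14 is too low whenever the off-schedule peak lies in a higher band than every value the table uses. For ALT in Table 2.18 after a scheduled trigger:

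- Baseline Grade 0, scheduled ALT of 3 or more: at least 2 − 0 = 2 grades, already counted.
- Baseline Grade 1, scheduled ALT above 5: at least 3 − 1 = 2 grades, already counted.
- Baseline Grade 1, scheduled ALT of 3 to 5: 2 − 1 = 1 grade, not counted. A later off-schedule value above 5 gives at least 3 − 1 = 2 grades and is missed.

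This assumes that Day 0 ALT is still below the 2 x ULN limit of exclusion criterion 16. AST, alkaline phosphatase and bilirubin are drawn at the same repeats; their grades are not worked through here.

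Assumed example: ALT 1.5 x ULN at baseline, 4.5 on Day 28 without symptoms or raised bilirubin, 6 at the weekly repeat on Day 35, and lower by Day 56. Table 2.14 would show Grade 2 instead of 3. Table 2.18 would count 0 subjects instead of 1.

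**5. Other panels.** Protocol 6.2.1 orders a blood count with differential after a liver event meeting criteria 1 to 3. It requires total IgG only when ALT and bilirubin are both raised. I found no order for off-schedule graded urinalysis.

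**6. Size of one case.** 1/20 = 5.0 points at the planned enrolment; 1/12 = 8.3 points at the minimum number of completers.

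**The case against.** **The rule may not apply.** The SAP does not define an unscheduled visit. Liver follow-up that the protocol requires could be read as planned; the protocol's own mention of unscheduled visits (6.2.3) concerns discretionary vital signs. This stands as an ambiguity, and it is a reason to settle the wording.

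**An exemption may sit elsewhere.** The shells for these tables are not supplied ("Data Display Specification will be made available on Request"), nor is the sponsor's reporting standard (IDSL). A display-specific rule would normally qualify a general one, and 11.5.1 allows for other specification. This stands as a limit: the finding covers the text supplied. Protocol 9.3.2, which puts all available data in the data sets, does not say which records a table uses. The SAP 11.3.3 promise to assess the impact of major timing deviations comes after the fact and exempts nothing.

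**Little is lost.** Values remain in Listings 19 to 22 and liver events in Listings 26 to 30. Clinically significant abnormalities not attributed to lupus become adverse events and can reach Tables 2.01 to 2.04. Raised ALT with raised bilirubin is an SAE. This stands, and it keeps the point minor.

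**The mechanism is narrow.** A reader might infer that every ALT rise brings a prompt repeat. Protocol 6.2.1 orders the 24-hour and 24-to-72-hour returns only for liver criteria 1 to 3; an isolated ALT of 3 to below 5 x ULN gets weekly monitoring. A reader might also infer that all eight tables are equally exposed. They are not: hematology and IgG are affected only through liver-event follow-up, and urinalysis has no such order.

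**Conclusion.** The point holds and is minor. Applied as written, SAP 11.3.3, 11.4.1 and 11.5.1 can lower the grade shown in tables meant to show the worst, and cannot raise it when baseline is fixed. Chemistry is the clearest case. Half or more of the weekly repeats fall off schedule in the upper case on either count. A missed ALT worsening in Table 2.18 after a scheduled trigger needs the specific baseline, trigger and peak set out in the working.

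A reader might take the draw shares as misgrading rates, or conclude that these tables will be wrong. The documents support neither. A grade changes only if the peak falls in an excluded or averaged record and in a higher band than the value used, and that cannot be known before data. The study is single-arm and descriptive, so no hypothesis test is affected.

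The conclusion assumes that liver follow-up draws are treated as unscheduled, or are averaged or displaced under 11.4.1, and that the unseen shells and standard contain no exemption.

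**What to change.** State in SAP 11.3.3, and as a programming note on Tables 2.14 to 2.21, that:

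- these tables take the single most severe post-dose result for each subject and parameter from all records: scheduled, unscheduled, repeat and out-of-window, and from withdrawn subjects, including protocol-required liver follow-up;
- this overrides the scheduled-visit and window rules in 11.3.3, the planned-data rule in 11.5.1 and the averaging and nearest-value rule in 11.4.1;
- the post-dose period ends at a stated point. This is needed because adverse event collection ends at Day 84 or discontinuation (protocol 7.1.1), while liver monitoring has no fixed end date.

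Keep the scheduled-visit restriction for by-visit and change-from-baseline tables.

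The cost is a short SAP addition, one programming note and a record flag. The values are already due in the listings, so no new data and no protocol amendment are needed.
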